3.4.1 Missing Question Imputation for Total Score

For all parent and child questionnaires if $\leq 10\%$ of questions are missing the following imputation algorithm will be implemented:

1. Sum the values of all completed questions
2. Divide by the number of completed questions
3. Multiply this value by the total number of questions available on the questionnaire

The number of questions that are allowed to be missing for each questionnaire are as follows:

1. PAID Questionnaires: 2 Questions
2. BGMC Questionnaire: 1 Question
3. DFCS Questionnaire: 2 Questions

3.4.2 PAID Questionnaires (PAID-TP, PAID-YP, PAID-T, PAID-C)

Each question ranges in response values between 1 and 6:

- Child version: 1-2 = 'Not a Problem', 3-4 are 'Medium Problem', and 5-6 are 'Big Problem'
- Teen or Parent versions: 1-2 = 'Not a Problem', 3-4 are 'Moderate Problem', and 5-6 are 'Serious Problem'
- Derived Total Score (26 questions) ranging between 26 and 156
- Derived change from baseline defined as:
$$\text{(Value at Visit - Baseline Value)}$$
- Derived % Change from baseline defined as:
$$\text{(Derived Change from baseline / Baseline Value) X 100.}$$

3.4.3 BGMC Questionnaire (Youth, Parent)

Each question ranges in response values between 1 and 3, where 1='Almost Never', 2='Sometimes', and 3='Almost Always'.

- Derived Total Score (8 questions) ranges between 8 and 24

- Derived change from baseline defined as:
(Value at Visit – Baseline Value)
- Derived % Change from baseline defined as:
(Derived Change from baseline / Baseline Value) X 100.

3.4.4 DFCS Questionnaire (Youth, Parent)

Each question ranges in response values between 1 and 3, where 1='Almost Never', 2='Sometimes', and 3='Almost Always'.

- Derived Total Score (19 questions) ranges between 19 and 57
- Derived change from baseline defined as:
(Value at Visit – Baseline Value)
- Derived % Change from baseline defined as:
(Derived Change from baseline / Baseline Value) X 100.

3.5 Derived Glycemic Control Parameters

3.5.1 HbA1c

At Visits 3 and 4 the following variables will be derived:

- Derived change from baseline defined as:
(Value at Visit – Baseline Value)
- Derived % Change from baseline defined as:
(Derived Change from baseline / Baseline Value) X 100.

3.5.2 Blood Glucose Data

Blood glucose readings from the downloaded Diasend meter files or the ACCU-CHEK® Connect DMS System data will be linked to a particular subject by means of the Subject ID number. Cross-checking between the serial number(s) entered into the eCRF and the serial number within each downloaded file will be done to check for missing files.

3.5.2.1 Derived Visit and Visit Intervals

The date of each visit from the eCRF data will be used as a reference date for the dates of BG readings from the subject BG files. Those readings from Diasend download files that occur on or 30 days prior to the baseline visit date will be considered Baseline values. In a similar fashion values between 30 days prior to or on Visit 3 or Visit 4 will be considered Visit 3 or Visit 4 values, respectively.

For Baseline downloads, if there are no readings on the 30th day prior to the visit date, the first day there is a reading will be considered the beginning of the Baseline visit interval. The length of the visit interval for baseline will be calculated as:

$(\text{Baseline Date} - \text{Date of First day of Baseline interval}) + 1$

Post-baseline intervals will be defined as 30 days for the Intervention group, and a similar length of visit interval as defined for Baseline will apply to the Control group.

It will be assumed that the first date reading for each subject using the ACCU-CHEK® Connect DMS System will be entered after training (post-baseline) even if on the same day as baseline.

3.5.2.2 Derived BG Glycemic Control Parameters

The following derivations will be made from the BG data at each study interval (Baseline, Visit 3, and Visit 4):

- Total number of BG checks during the interval
- SMBG frequency: Average number of daily SMBG measurements per interval will be defined as the total number of BG checks during the visit interval divided by the total number of days in the interval.
- BG Range Flags: Individual BG readings will be flagged as:
 - hypoglycemic reading if < 70 mg/dl (LO)
 - hyperglycemic reading if > 160 mg/dl (HI)
 - within target range 70-160 mg/dl

- Hypoglycemia: Percentage of hypoglycemic measurements defined as the number of hypoglycemic readings in the interval divided by the total number of BG checks in the interval.
- Glucose Target Range: Percentage of Target Range measurements defined as the number of within target range readings in the interval divided by the total number of BG checks in the interval. Values designated as ‘LO’ or ‘HI’ in the meter data will be classified as below or above, respectively
- Glycemic Variability
 - Mean of all BG readings per subject within the interval
 - BG variability (as SD of all glucose readings over the interval)

4 DATA SETS TO BE ANALYZED (STUDY POPULATIONS)

4.1 Full Analysis Set (FAS)

The Full Analysis Set Population (FAS) will be all eligible families that have signed an informed consent and completed (with the acceptable level of missing questions to calculate a total score – see section 3.4.1) all questions on the PAID Parent (YP or TP) Questionnaire at both baseline and Visit 4.

4.2 Intent-to-Treat Population (ITT)

The Intent-to-Treat Population (ITT) will be all families that have signed informed consent, and completed (with the acceptable level of missing questions to calculate a total score – see section 3.4.1) at least one Questionnaire (PAID-YP, PAID-TP, PAID-C, PAID-T, BGMC-Y, BGMC-P, DFCS-Y, DFCS-P), at both Baseline and Visit 4.

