11.2 Populations for Analysis

The intent-to-treat (ITT) population will consist of all families that have completed at least one questionnaire at both baseline and end of study.

The full analysis set (FAS) will consist of all families that have completed the parent/caregiver PAID-PR questionnaire at both baseline and end of study.

The safety population will consist of all subjects.

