11.4 Primary Objective Analysis

Change in diabetes-related distress in parents/caregivers of children who utilize the ACCU-CHEK® Connect Diabetes Management system compared to the change observed in the Control Group. Diabetes related distress will be measured via the PAID- C & T parent questionnaires which will be administered Pre and Post Study Participation.

A change in the total PAID-C & T parent score between pre and post study will be calculated and compared between groups utilizing with treatment group as the independent variable, and covariates such as baseline PAID, and child demographic and diabetes history variables.

Descriptive statistics for observed and change from baseline scores, and 2-sample t-tests will be presented at both 3 and 6 month visits. This analysis will be performed on the Full Analysis Set population.

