11.5 Secondary Objective(s) Analysis

The following secondary objectives will be analyzed by comparing the Pre-Post changes in questionnaire scores from subjects utilizing the ACCU-CHEK® Connect Diabetes Management system with changes from those subjects in the Control Group. Pre, Post, and Change scores will be calculated for each group and summarized by descriptive statistics. The change scores will be compared between groups utilizing both ANCOVA methods described above, and with 2-sample t-tests. These analyses will be performed on both the FAS and the ITT populations.

- Change from baseline in PAID- C & T parent at 3 months in parents/caregivers.
- Change from baseline in diabetes-related family conflict in parents/caregivers as measured by DFCS questionnaires at 3 and 6 months

- Change from baseline in attitudes toward blood glucose monitoring in parents/caregivers as measured by BGMC-parent questionnaire at 3 and 6 months.
- Change from baseline in diabetes-related distress among school-age children as measured by the PAID- C & T child questionnaires at 3 and 6 months.
- Change from baseline in perceived family conflict among school-age children measured by the DFCS-youth questionnaire at 3 and 6 months.
- Change from baseline in affect toward blood glucose monitoring (BGM) among school-age children as measured by the BGMC-youth questionnaire at 3 and 6 months.
- Change from baseline in perceived family conflict in parent/caregiver as measured by DFCSparent questionnaire at 3 and 6 months.
- Changes from baseline in glycemic control at 3 and 6 months defined as:
 - o HbA1c
 - Percentage in Glucose Target Range
 - o Glycemic Variability
 - Hypoglycemia
- The secondary objectives of ease of use, satisfaction, and preference for using the ACCU-CHEK® Connect Diabetes Management System compared with previous systems will be analyzed by summarizing the end of study outcomes from the following participant groups within the intervention group:
 - o Parent
 - o Children
 - School staff
 - Healthcare Provider (s)

Each question from this Post Questionnaire will be summarized separately utilizing descriptive statistics of the numerical scale value of the question (mean, standard deviation, range and 95% CI), and the distribution of values (number and percent of respondents at each level of response). These analyses will be performed on both the FAS and the ITT populations

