4.3 Interim Full Analysis Set (IFAS)

The Interim Full Analysis Set Population (IFAS) will be all eligible families that have signed an informed consent and completed (with the acceptable level of missing questions to calculate a

total score – see section 3.4.1) all questions on the PAID Parent (YP or TP) Questionnaire at both baseline and Visit 3.

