4.4 Interim Intent-to-Treat Population (IITT)

The Interim Intent-to-Treat Population (IITT) will be all eligible families that have signed informed consent, and completed (with the acceptable level of missing questions to calculate a total score – see section 3.4.1) at least one Questionnaire (PAID-YP, PAID-TP, PAID-C, PAID-T, BGMC-Y, BGMC-P, DFCS-Y, DFCS-P), at both Baseline and Visit 3.

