6 TABLES

Table No.	Title
Table 1.1	Analysis Populations
Table 1.2.1	Demographics and Baseline Characteristics Parent/Caregiver of Child with Diabetes FAS Population
Table 1.2.2	Demographics and Baseline Characteristics Parent/Caregiver of Child with Diabetes ITT Population
Table 1.3.1	Diabetes Management, Communication and Diabetes Related Absences Parent of Child with Diabetes FAS Population
Table 1.3.2	Diabetes Management, Communication and Diabetes Related Absences Parent of Child with Diabetes ITT Population
Table 1.4.1	Demographics and Baseline Characteristics Child with Diabetes FAS Population
Table 1.4.2	Demographics and Baseline Characteristics Child with Diabetes ITT Population
Table 1.5.1	Diabetes Management, Communication and Diabetes Related Absences Child with Diabetes FAS Population
Table 1.5.2	Diabetes Management, Communication and Diabetes Related Absences Child with Diabetes

Roche Diabetes Care, Inc

Table No.	Title
	ITT Population
Table 1.6.1	Summary of Family Disposition Safety Population
Table 1.7.1	Summary of PAID Questionnaire Completion FAS Population
Table 1.7.2	Summary of PAID Questionnaire Completion ITT Population
Table 1.8.1	Summary of BGMC Questionnaire Completion FAS Population
Table 1.8.2	Summary of BGMC Questionnaire Completion ITT Population
Table 1.9.1	Summary of DFCS Questionnaire Completion FAS Population
Table 1.9.2	Summary of DFCS Questionnaire Completion ITT Population
Table 2.1.1	Primary Analysis - PAID - Parent Questionnaire Change from Baseline to Visit 4 in TOTAL PAID SCORE FAS Population
Table 2.2.1.1	Secondary Analysis - PAID - Parent Questionnaire Change from Baseline to Visit 3 in TOTAL PAID SCORE FAS Population
Table 2.2.1.2	Secondary Analysis - PAID - Parent Questionnaire Change from Baseline to Visit 3 in TOTAL PAID SCORE ITT Population
Table 2.2.2.1	Secondary Analysis - PAID - Child Questionnaire Change from Baseline TOTAL PAID SCORE FAS Population
Table 2.2.2.2	Secondary Analysis - PAID - Child Questionnaire Change from Baseline TOTAL PAID SCORE ITT Population
Table 2.2.3.1	Secondary Analysis - PAID - Teen Questionnaire Change from Baseline TOTAL PAID SCORE FAS Population
Table 2.2.3.2	Secondary Analysis - PAID - Teen Questionnaire Change from Baseline TOTAL PAID SCORE ITT Population

Roche Diabetes Care, Inc

Table No.	Title
Table 2.3.1.1	Secondary Analysis - BGMC - Parent Questionnaire Change from Baseline TOTAL BGMC SCORE FAS Population

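### As written, the SAP's FAS and its ITT set both need a scorable Visit 4 questionnaire, so every between-group efficacy result, including those at 3 months, is a completer analysis

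*SAP*

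**What the plan says.** **The two efficacy sets.** SAP 4.1 defines the FAS by completion, within the allowed missing items, of "all questions on the PAID Parent (YP or TP) Questionnaire at both baseline and Visit 4". SAP 4.2 defines the ITT population by "at least one Questionnaire (PAID-YP, PAID-TP, PAID-C, PAID-T, BGMC-Y, BGMC-P, DFCS-Y, DFCS-P), at both Baseline and Visit 4", under the same missing-item rule. Protocol 11.2 is looser about timing: "The intent-to-treat (ITT) population will consist of all families that have completed at least one questionnaire at both baseline and end of study".

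**Where they are used.** SAP 5.5.1 puts the primary analysis on the FAS. SAP 5.5.2 puts every secondary analysis, at 3 and 6 months and including glycemic control, on FAS and ITT. SAP 4.6 uses the same two sets for meter data, less subjects who fail its baseline-data rule. Protocol 11.4 agrees for the parent PAID ("2-sample t-tests will be presented at both 3 and 6 month visits. This analysis will be performed on the Full Analysis Set population"), as does 11.5 for the secondary endpoints ("These analyses will be performed on both the FAS and the ITT populations"). The SAP 6 table list follows suit. The first 3-month parent PAID table is titled "Change from Baseline to Visit 3 in TOTAL PAID SCORE FAS Population", and its companion is the ITT version.

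**The Visit 3 sets.** SAP 4.3 defines an interim FAS ("The Interim Full Analysis Set Population (IFAS) will be all eligible families that have signed an informed consent", with a scorable parent PAID at baseline and Visit 3). SAP 4.4 defines an interim ITT set by "at least one Questionnaire (PAID-YP, PAID-TP, PAID-C, PAID-T, BGMC-Y, BGMC-P, DFCS-Y, DFCS-P), at both Baseline and Visit 3". Neither is named in SAP 5.5 or in any table title in SAP 6.

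**Missing data.** SAP 3.4 and 3.4.1 fill in missing items within a questionnaire. Nothing deals with a missing visit. Protocol 6.3 asks early leavers to attend for a completion form and a questionnaire. The SAP does not say where that questionnaire goes.

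**The concern.** Two things are at stake.

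- **3 months.** Membership of both sets is decided at Visit 4, about three months after the 3-month data were collected. Valid 3-month scores, HbA1c results and meter data are discarded because of something that happened later. This loses information and makes the 3-month comparison conditional on staying to the end.
- **6 months.** The trial is unblinded and its primary endpoint is self-reported. Protocol 6.3 withdraws families for non-compliance and for starting CSII, CGM or remote data sharing, which could remove families from either arm for reasons connected with distress. A set labelled intent-to-treat that holds only families with Visit 4 data tells the reader that this has been dealt with when it has not.

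For the 6-month parent PAID the ITT set offers no second view. Only an FAS table is listed. A family with scorable parent PAID at baseline and Visit 4 is already in the FAS unless it is ineligible, because SAP 4.1 is restricted to eligible families and SAP 4.2 is not.

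**Working it through.** **1. Trace one family.** Take an eligible family with scorable questionnaires, HbA1c and meter data at baseline and Visit 3, and no questionnaire coded as Visit 4.

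| Set | Visit condition | Family included? | Named in an efficacy section or listed table? |
|---|---|---|---|
| FAS (SAP 4.1) | Baseline and Visit 4 | No | Yes |
| ITT (SAP 4.2) | Baseline and Visit 4 | No | Yes |
| IFAS (SAP 4.3) | Baseline and Visit 3 | Yes | No |
| IITT (SAP 4.4) | Baseline and Visit 3 | Yes | No |

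The family contributes to no between-group efficacy result, although change at 3 months is a stated secondary objective.

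**2. Reproduce the plan's sample size.** Inputs from Protocol 11.1: effect 0.460, two-sided 0.05, 75 per group, 80% power. For a two-sample t-test the noncentrality is 0.46 × √(n/2), with 2n − 2 degrees of freedom.

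- n = 75: 0.46 × √37.5 = 2.817; df 148; critical value 1.976; power 79.9%. The plan's 80% is reproduced.
- Enrolment of 100 for 75 evaluable implies an allowance of (100 − 75)/100 = 25%.

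**3. Families at stake at 3 months.** The documents give no dropout by arm or by time. If all 25 losses per arm come before Visit 3, no usable 3-month data are lost. If all come after Visit 3, 25 families per arm are lost. The range is therefore 0 to 25 per arm at 100 enrolled per arm.

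**4. What that means for 3-month power.** The plan gives 0.46 for the 6-month endpoint only; using it at 3 months is an assumption. Clustering is ignored here and would lower every figure.

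| Families per arm | When losses occur | Noncentrality | Power |
|---|---|---|---|
| 75 | analysed as planned | 2.817 | 79.9% |
| 87 | about half after Visit 3 | 0.46 × √43.5 = 3.034 | 85.5% |
| 100 | all after Visit 3 | 0.46 × √50 = 3.253 | 89.9% |

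At best the standard error shrinks by the factor √(75/100) = 0.866, or 13.4%.

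**5. Bias at 6 months.** Let p be the fraction lost in an arm and d the completer-minus-leaver difference that remains after covariate adjustment. The completer contrast differs from that in all families by p(I) × d(I) − p(C) × d(C). The documents supply neither p by arm nor d, so two assumed cases only show the scale:

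- 25% lost in both arms, d = 0.5 SD in both: 0.25 × 0.5 − 0.25 × 0.5 = 0.
- 30% against 20% lost, d = 0.5 SD in both: 0.15 − 0.10 = 0.05 SD, or 0.25 points at SD 5 and 0.80 at SD 16. Swapping the arms reverses the sign.

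These are illustrations, not bounds.

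**The case against.** Much of the case on the other side stands, and it limits the point.

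- **Exit questionnaires.** Protocol 6.3 collects one and Protocol 11.2 refers only to study end, so some leavers could be included if it is coded as Visit 4. A reader might infer that the SAP's wording rules this out. It does not; the SAP is silent, and the completer reading holds only unless such coding is applied.
- **The Visit 3 sets.** A reader might infer that they are never used. The documents do not show that. They may serve the data pull in Protocol 11.7, SAP 5.1 and 5.2 could cover them in counts and baseline summaries, and the output templates are in a separate document. What can be said is that no efficacy section or listed table names them.
- **HbA1c and glucose at 6 months.** These are collected at the same visit as the questionnaires, and any one of eight instruments admits a family to ITT. The loss there is likely small; it matters mainly at 3 months.
- **Same families at both times.** This is a legitimate choice for comparing time points, and worth keeping as supportive.
- **Transparency.** SAP 5.1 and 5.4 report exclusions and discontinuations by arm. This would reveal unequal loss but would not correct for it.
- **Bias.** A reader might infer that the 6-month result is biased. The documents do not show it. Loss that depends only on baseline PAID, age and duration leaves a correctly specified ANCOVA unbiased. It is also tempting to quote a tipping point using SE = √(2/75) and 148 degrees of freedom. Only 8 to 13 sites are randomised, so that calculation would overstate how robust the result is, and none is given here.

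**Conclusion.** The point stands for the SAP as written: both efficacy sets depend on Visit 4, every between-group efficacy analysis uses them, and the label intent-to-treat does not fit. This rests on exit questionnaires not being coded as Visit 4.

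The 3-month consequence is definite in kind and uncertain in size: 0 to 25 families per arm, assuming 100 enrolled per arm. The plan allows 150 to 200 in total, so enrolment may be smaller. The corresponding power range of 79.9% to at most 89.9% assumes an effect of 0.46 at 3 months and no clustering. At 6 months bias is possible, with size and direction unknown. The plan should be changed, but nothing here shows that its primary conclusion would be wrong. Confidence is high in the reading of the definitions, and lower in any figure for the consequences.

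**What to change.** 1. **3-month endpoints.** Analyse each on all eligible families with baseline and Visit 3 data for that endpoint (IFAS and IITT for questionnaires). Do not make HbA1c or glucose analyses depend on a Visit 4 questionnaire. Keep the same-families version as supportive.
2. **6-month parent PAID.** Label the FAS and ITT results as completer analyses and drop the intent-to-treat name. Add an analysis of all eligible enrolled families by their site's randomised arm, using every family with a baseline and any post-baseline score. Use a repeated-measures model of Visits 3 and 4 with the planned covariates, a site random effect, and small-sample degrees of freedom based on the number of sites. State three limits: it assumes missing at random; for families withdrawn on starting CSII, CGM or remote sharing it estimates the outcome as if they had stayed, so it is not an unqualified intention-to-treat effect; and enrolment followed known site allocation (Protocol 5), which the model does not cure.
3. **Sensitivity.** Add one missing-not-at-random analysis that shifts the leavers' mean in one arm, uses the site-adjusted standard error, and reports the shift at which the conclusion changes.
4. **Wording.** Reconcile Protocol 11.2 with SAP 4.1 and 4.2 on the time point, and state whether the Protocol 6.3 exit questionnaire counts as Visit 4.

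The cost is wording in both documents and modest programming on data already collected; no new visits are needed. Missing at random cannot be verified, and outcomes not collected after withdrawal cannot be recovered.

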4.3 Interim Full Analysis Set (IFAS)

The Interim Full Analysis Set Population (IFAS) will be all eligible families that have signed an informed consent and completed (with the acceptable level of missing questions to calculate a

total score – see section 3.4.1) all questions on the PAID Parent (YP or TP) Questionnaire at both baseline and Visit 3.

4.4 Interim Intent-to-Treat Population (IITT)

The Interim Intent-to-Treat Population (IITT) will be all eligible families that have signed informed consent, and completed (with the acceptable level of missing questions to calculate a total score – see section 3.4.1) at least one Questionnaire (PAID-YP, PAID-TP, PAID-C, PAID-T, BGMC-Y, BGMC-P, DFCS-Y, DFCS-P), at both Baseline and Visit 3.

4.5 Safety Population (SAF)

The Safety Population (SAF) will be all eligible families that have signed informed consent/assent and exited the study after participating for at least 1 day in the study.

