6.2 Exclusion Criteria

Subjects may not participate in this clinical study if they and/or their parents/caregivers meet **ANY** of the respective criteria:

Child/adolescent with Diabetes:

- On CSII or intending to transition from MDI to CSII during study period
- CGM use during the course of the study (both home and/or professional CGM)
- Remote data sharing system/device use during the course of the study (i.e. NightScout, DexCom Share, Medtronic Connect)
- Pregnancy
- Diagnosed with any clinically significant condition (e.g. anemia, major organ system disease, infections, psychosis or cognitive impairment);
- Chronic use of steroids in adrenal suppressive doses, other immuno-modulatory medication or chemotherapy

Parents/Caregivers and child with Diabetes

- Visual impairment; preventing the complete use of Connect system
- Parent/caregiver is the investigator or any sub-investigator, general practitioner, practice staff, pharmacist, research assistant or other staff or relative of those directly involved in the conduct of the study and design of the protocol.

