6.3 Point of Enrollment and Withdrawal

A subject is considered enrolled in the study as soon as

- His/her parents/caregivers have signed the Informed Consent and
- 18 year old with diabetes has signed the Informed Consent (NOTE: parental consent is not required if 18 years of age at time of study entry)
- Child with diabetes has signed age-appropriate child assent
- Child/adolescent with diabetes has been deemed eligible according to above inclusion/exclusion criteria.

A subject is considered withdrawn if he/she was first enrolled, and thereafter one or more of the following occurs:

- Screening failure (any reason).
- Withdrawal of consent to participate in the study.

- Non-compliance with the protocol procedures
- Subject begins CSII therapy during the course of study participation
- Subject begins CGM during the course of study participation
- Subject begins remote data sharing system/device during the course of study participation
- Subject becomes pregnant (self-reported)
- Investigator determines it is not in the best interest of the subject to continue participation in the study.

If any of the above occurs, the Investigator will:

Ensure subject presents at site accompanied by parents/caregivers in order to ensure complete
documentation (Study Completion Form in the eCRF including the date of and reason for early
discontinuation and questionnaire), and to return all study materials.

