5 STATISTICAL ANALYSES

5.1 Study Populations

The number and percentage of families within each analysis population and treatment group will be summarized overall and by exclusion reason from each population. The denominator for each population will be the Safety Population.

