Table 2.7.2.2	Exit Questionnaire: Usability Child with Diabetes ITT Population
Table 2.8.1.1	Exit Questionnaire: Satisfaction Parent/Caregiver of Child with Diabetes FAS Population
Table 2.8.1.2	Exit Questionnaire: Satisfaction Parent/Caregiver of Child with Diabetes ITT Population
Table 2.8.2.1	Exit Questionnaire: Satisfaction Child with Diabetes FAS Population

Roche Diabetes Care, Inc

Table No.	Title
Table 2.8.2.2	Exit Questionnaire: Satisfaction Child with Diabetes ITT Population
Table 2.9.1.1	End of Study Questionnaire: Preference Parent/Caregiver of Child with Diabetes FAS Population
Table 2.9.1.2	End of Study Questionnaire: Preference Parent/Caregiver of Child with Diabetes ITT Population
Table 2.9.2.1	End of Study Questionnaire: Preference Child with Diabetes FAS Population
Table 2.9.2.2	End of Study Questionnaire: Preference Child with Diabetes ITT Population
Table 2.10.1.1	School Nurse Questionnaire: Preference FAS Population
Table 2.10.1.2	School Nurse Questionnaire: Preference ITT Population
Table 2.10.2.1	School Nurse Questionnaire: Usability FAS Population
Table 2.10.2.2	School Nurse Questionnaire: Usability ITT Population
Table 2.10.3.1	School Nurse Questionnaire: Satisfaction FAS Population
Table 2.10.3.2	School Nurse Questionnaire: Satisfaction ITT Population
Table 2.11.1.1	HCP Questionnaire: Preference FAS Population
Table 2.11.1.2	HCP Questionnaire: Preference ITT Population
Table 2.11.2.1	HCP Questionnaire: Usability FAS Population
Table 2.11.2.2	HCP Questionnaire: Usability ITT Population
Table 2.11.3.1	HCP Questionnaire: Satisfaction HCP Eligibility Population
Table 3.1	Summary of All Adverse Events by MedDRA SOC and Preferred Term Safety Population

Roche Diabetes Care, Inc

Table No.	Title
Table 3.2.1	Summary of All Adverse Events by Maximum Severity Safety Population
Table 3.2.2	Summary of All Adverse Events by Strongest Causality to Study Device Safety Population
Table 3.2.3	Summary of All Adverse Events Leading to Withdrawal from the Study Safety Population
Table 3.3	Summary of Symptomatic Hypoglycemia, Severe Hypoglycemia and Diabetic Ketoacidosis Safety Population

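### The SAP limits the safety population to eligible families that exited, while the protocol takes all subjects, so late screening failures and families lost without an exit record can drop out of the by-arm tables

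*SAP*

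**What the plan says.** Protocol 11.2 sets no conditions: "The safety population will consist of all subjects". SAP 4.5 sets several. Its safety population "will be all eligible families that have signed informed consent/assent and exited the study after participating for at least 1 day". The SAP does not define eligible or exited and does not explain the change.

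The set is used widely in the SAP:

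- Adverse events: Table 3.1 ("Summary of All Adverse Events by MedDRA SOC and Preferred Term Safety Population"), Tables 3.2.1 to 3.2.3, and Table 3.3, which covers symptomatic and severe hypoglycemia and diabetic ketoacidosis.
- Disposition: Table 1.6.1 ("Summary of Family Disposition Safety Population").
- Population counts, SAP 5.1: "The denominator for each population will be the Safety Population".

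The ITT definition in SAP 4.2 begins differently, with no eligibility condition: "The Intent-to-Treat Population (ITT) will be all families that have signed informed consent".

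Under Protocol 6.3, a subject is enrolled once consent and assent are in place and the child has been judged eligible. Among the reasons for withdrawal after enrollment, the same section lists "Screening failure (any reason". Protocol 7.2 puts the eligibility check and, at intervention sites, device dispensing and training at the same visit.

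**The concern.** Membership of a safety set should rest on facts fixed at entry, such as consent and the start of study procedures. It should not rest on a later judgement about eligibility or on whether a form was completed at the end. The SAP wording allows both to decide who is counted.

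No other final-analysis set can make up the loss. FAS and ITT both require a completed questionnaire at Visit 4 (SAP 4.1 and 4.2), so they leave out most early leavers by construction. The safety population is the only final set that can hold those families and their events. If it is narrowed, the by-arm incidence of adverse events and the account of who left, and why, are both incomplete.

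**Working it through.** The documents state no figure for this point, so the check is a comparison of definitions followed by a labelled illustration.

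**1. Compare the two definitions.** The protocol requires only that the person is a subject. The SAP adds eligibility, exit, and at least 1 day of participation. The SAP set can therefore be smaller than the protocol set and cannot be larger.

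**2. Can the eligibility condition remove an exposed child?** Yes. Protocol 6.3 requires a child to be judged eligible in order to be enrolled, and then lists screening failure among events that follow enrollment. The protocol thus foresees a favourable eligibility decision being reversed. At an intervention site the device may already have been dispensed at Visit 1.

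**3. Can the exit condition remove a family?** Possibly. Protocol 6.3 expects a withdrawn subject to attend the site with parents or caregivers so that the Study Completion Form can be filled in. A family lost to follow-up may not attend. If exit means that such a record exists, that family is outside the set.

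**4. Does the 1-day condition matter?** Probably very little. SAP 3.3 counts Visit 1 as Day 1, so attending baseline plausibly satisfies it.

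**5. Is the denominator coherent?** Not fully. SAF, FAS, IFAS and IITT all carry the word eligible (SAP 4.1 and 4.3 to 4.5), but ITT does not. A family found ineligible only at or after Visit 4, with usable questionnaires at baseline and Visit 4, is in ITT but not in SAF, although SAP 5.1 makes SAF the denominator for ITT.

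**6. Illustration of size (assumed inputs).** From SAP 2.1.2, take 100 per group. Assume k device-arm children are later ruled ineligible, each with the same independent risk p of an adverse event. The chance that at least one child with an event is left out is 1 − (1 − p)^k.

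| k | Denominator | p = 5% | p = 20% |
|---|---|---|---|
| 1 | 99 | 5% | 20% |
| 3 | 97 | 1 − 0.95³ = 14% | 1 − 0.80³ = 49% |
| 5 | 95 | 23% | 67% |
| 10 | 90 | 40% | 89% |

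The effect on a tabulated rate is small when k is small. Suppose 10 of 100 children have an event (10.0%) and k = 3. If none of the three excluded had an event, the table shows 10/97 = 10.3%. If all three did, it shows 7/97 = 7.2%.

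**The case against.** The best defence is that eligible simply means judged eligible at Visit 1. Protocol 6.3 makes that part of being enrolled, so SAP 4.5 would be describing enrolled families. On this view the 1-day condition is met by attending baseline, and exit covers anyone with a completion or discontinuation record. Nor are serious events lost from reporting: Protocol 11.6 asks for deaths, other SAEs and AEs leading to withdrawal to be listed separately, and SAP Listings 15.x and 17 name no population. The eligibility check and pregnancy test also come before dispensing in the Visit 1 list, which should keep late reversals rare.

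Most of this stands as an argument about size. It does not remove the conflict, because the SAP never says that eligibility is fixed at Visit 1, and Protocol 6.3 itself provides for screening failure after enrollment. A listing also does not replace incidence by arm.

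A reader might infer something stronger. Protocol 6.2 words one exclusion as "CGM use during the course of the study (both home and/or professional CGM", so a child who starts CGM in mid-study, perhaps after severe hypoglycemia, might seem to become ineligible and take that event out of the tables. The documents do not support this. Protocol 6.3 lists starting CGM, CSII or remote data sharing as withdrawal reasons separate from screening failure, and SAP 2.1.1 words CGM and remote-sharing use as status at entry. Such a child was eligible, took part for more than a day, and exited by withdrawal. The child stays in the safety population and in the disposition table.

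**Conclusion.** The conflict between SAP 4.5 and Protocol 11.2 is real, and its reach is narrow. It concerns enrolled children later declared screening failures and families lost without an exit record. For these, events and departures can be missing from the by-arm adverse event tables and the disposition table, and the ITT count can include families outside its stated denominator.

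The documents give no frequency, overall or by arm, so no bias can be estimated. The cases are probably few, and the illustration shows only what a handful could do under assumed risks. Device exposure occurs in one arm only, so any loss of exposed children falls there, but nothing in the documents shows that late screening failure is more common in that arm. The conclusion assumes that the SAP would be applied as written; if eligible was meant as judged eligible at Visit 1, the SAP needs to say so. The primary analysis uses the FAS (SAP 5.5.1) and is untouched. Severity: minor, an alignment of the SAP with the protocol.

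**What to change.** In SAP 4.5, delete the eligibility, exit and 1-day conditions. Define the safety population as all subjects with signed informed consent, and assent where age requires it, who began Visit 1 study procedures, by allocated site group, regardless of later eligibility findings or whether a completion form exists. The assent wording matters because Protocol 6.1 asks for no assent from 6-year-olds. Tying the set to the start of Visit 1 procedures is safer than tying it to enrollment, which under Protocol 6.3 already depends on eligibility.

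Use this set as the denominator for Tables 1.1 and 1.6.1, and show screening failure after enrollment and loss to follow-up as separate discontinuation reasons. The wider set also takes in any family that fails screening during Visit 1 before enrollment; give these their own line so that they are not mistaken for exposed children.

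The cost is SAP wording and table footnotes. No new data collection is needed. Make the change before the safety tables are run, so that the choice between readings is not made with the events in view.
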